- Is there a reduced ability to maintain and shift attention?

Feature 3. Disorganized Thinking

- Was the patient's thinking disorganized or incoherent, such as rambling or irrelevant conversation, unclear or illogical flow of ideas, or unpredictable switching from subject to subject?
- Was the patient able to follow questions and commands throughout the assessment?

Feature 4. Altered Level of Consciousness

- Any level of consciousness other than 'alert'.
- Alert-normal, spontaneous fully aware of environment and interacts appropriately.
- Vigilant-hyperalert
- Lethargic-drowsy but easily aroused, unaware of some elements in the environment, or not spontaneously interacting appropriately with the interviewer; becomes fully aware and appropriately interactive when prodded minimally
- Stupor-difficult to arouse, unaware of some or all elements in the environment, or not spontaneously interacting with the interviewer; becomes incompletely aware and inappropriately interactive when prodded strongly
- Coma – unarousable, unaware of all elements in the environment, with no spontaneous interaction or awareness of the interviewer, so that the interview is difficult or impossible event with maximal prodding

7. ICU Length of stay [Time Frame: ICU stay]

ICU length of stay is calculated from time of ICU admission to time and date of actual discharge.

To be assessed up to ICU discharge.

8. Hospital Re-admission Rates [Time Frame: 6-months]

To be assessed up to 6-months post-surgery. Count and proportion of patients who were admitted to hospital more than once.

9. Hospital Length of stay [Time Frame: hospitalization]

Hospital length of stay will be calculated from the date of index surgical procedure to time and date of discharge from hospital.

To be assessed up to hospital discharge.

10. 6-Month Survival [Time Frame: 6-months]

Kaplan-Meier curves of and hazard ratio of survival over 6 months starting with day of surgery.

11. Quality of Life [Time Frame: day 30, 3-months and 6-months]

The SF-36 physical and mental summary scales will be analyzed separately.

Barthel Index of Activities of Daily Living Total Score

Frailty Scale

12. Return to work [Time Frame: 6-months]

Assessed using a questionnaire to determine the patient's ability to return to their pre-operative working capabilities. To be assessed up to 6 months post-surgery.

13. 6-minute walking test [Time Frame: hospital discharge]

This was done in a sub-study of pre specified patients.

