6.2.2 Secondary outcomes

Secondary binary outcomes such as cardiovascular complications, postoperative delirium, re-admissions, hospital-acquired infections and 30-day mortality will be compared between groups by a logistic mixed effects model with site included as a random effect.¹ Odds ratios with 95% confidence intervals will be reported.

Six-month mortality will be described by group using Kaplan-Meier curves. Survival will be compared by a hazard ratio with 95% confidence intervals and corresponding Wald test. Estimates will be derived from the Cox proportional hazards model with a random frailty for site. If the proportional hazards assumption is clearly and meaningfully violated, we will report a smoothed time dependent hazard ratio over time. However, the aforementioned overall Wald test will remain the primary test of statistical significance. Patients will be censored at the earliest of 183 days post randomization or last known follow-up.

Length of ICU and hospital stay will be summarized by arm using the quartiles of time to live discharge estimated from the subdistribution cumulative incidence function (CIF) where death is treated as a competing risk precluding the possibility of discharge. The between arm difference in time to live discharge will be tested using the Wald test from the Cox proportional hazards model with site as a random frailty to account for potential between site heterogeneity. Patients who die prior to discharge will be censored after the end of the follow-up period to account for the competing risk of death. This will yield virtually the same results as the Fine and Gray approach treating death as a competing risk precluding discharge, except we will have incorporated ICU as a random effect. This outcome is also known as time-to-discharge-alive (TTDA).

The SF-36, Barthel Index and frailty scale will be collected at baseline. At 30 days, 3 months and 6 months after surgery, we will repeat the Barthel Index and SF-36 and collect return to work data. The SF-36 physical and mental summary scales and the Barthel index will be treated as continuous variables and analyzed using a linear mixed effects model for longitudinal data. In order to include all patients

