with a baseline assessment regardless of follow-up, we will use constrained longitudinal data analysis where the independent dummy variable indicating treatment arm (1-treatment or 0-control) will be set so to 0 at baseline for both arms but 1 post baseline for the intervention arm.^{2,3} This model will include site as a random effect and will allow for unstructured within patient correlation as estimated by restricted maximum likelihood. The focus of these secondary analyses will be primarily descriptive as these outcomes are limited to survivors and no imputation for decedents is planned. Thus, these outcomes will not be informative of treatment efficacy if they are in the opposite direction from survival. The between group difference in the change from baseline to the various follow-up time points will be described as expected means with 95% confidence intervals.

6.2.3 Additional outcomes:

Days alive and home in 6 months will be analyzed using the same approach as PFDs.

Variables collected but not specifically listed above will be described by arm at each time they were collected using counts and percentages for categorical variables and medians and quartiles or means and standard deviations for continuous variables. Post baseline differences in these variables will be tested using the Cochran-Mantel-Haenszel test stratified by site for the categorical variables and the van Elteren test stratified by site for continuous variables. Analysis of these variables will be considered exploratory so no adjustment for multiplicity will be applied to p-values, but multiplicity of tests will be considered in when interpreting these results.

Study reporting will be in accordance with the CONSORT statement.⁴

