6.2.4 Adjustment for covariates

Analysis involving hypothesis testing or creation of confidence intervals will control for site which was the sole stratification factor at randomization. No other covariates will be controlled for.

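### The default test in SAP 6.2.3, with the site-only rule in 6.2.4, discards the patient's own baseline where one exists; the eight SF-36 domain scores are the clearest case, and the cost is precision only

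*SAP*

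**What the plan says.** **Default (6.2.3).** The scope is set by "Variables collected but not specifically listed above will be described by arm at each time they were collected". The rule for categorical variables reads: "Post baseline differences in these variables will be tested using the Cochran-Mantel-Haenszel test stratified by site for the categorical variables". Continuous variables get a van Elteren test, again stratified by site. Neither has a place for a baseline value. The status is also given: "Analysis of these variables will be considered exploratory so no adjustment for multiplicity will be applied to p-values".

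**Covariates (6.2.4).** Site is controlled for as the only stratification factor. The section then closes the list: "No other covariates will be controlled for".

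**Scales that do use baseline (6.2.2).** "The SF-36 physical and mental summary scales and the Barthel index will be treated as continuous variables", and they are analysed with a constrained longitudinal model. That model treats the baseline score as one of the repeated outcomes, with a common mean in both arms.

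**SF-36 domains.** Section 5.5 lists all eight domains and both summary scales at baseline. Section 6.2.2 repeats the SF-36 at 30 days, 3 months and 6 months. Sections 6.1.2 and 6.2.2 name only the two summary scales for analysis.

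**Frailty Scale.** Section 6.1.2 places it in secondary outcome 11, headed "Quality of Life [Time Frame: day 30, 3-months and 6-months". Section 6.2.2 says "The SF-36, Barthel Index and frailty scale will be collected at baseline", but its next sentence names only the Barthel Index and the SF-36 as repeated. No analysis method names frailty.

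**The concern.** With randomisation, a comparison of raw follow-up values is unbiased on average, but it carries all the between-patient variation that was already present before treatment. It also carries any chance imbalance in baseline into the result. The plan accepts the value of baseline for the SF-36 summaries and the Barthel Index and gives up the same information elsewhere without giving a reason. For the SF-36, a summary score and the domains of the same questionnaire, from the same patients and visits, would be tested on different footings. A summary and its domains could then appear to disagree partly because one comparison is noisier than the other.

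**Working it through.** **Which variables are affected.** To lose precision here, a variable needs a pre-treatment value, a planned post-baseline comparison, and no method other than the 6.2.3 default.

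| Variable | Pre-treatment value | Post-baseline comparison | Method |
|---|---|---|---|
| SF-36 summaries, Barthel | yes (5.5, 6.2.2) | yes (6.2.2) | longitudinal model; baseline used |
| SF-36 domains (8) | yes (5.5) | SF-36 repeated (6.2.2) | none named; default by the wording of 6.2.3 |
| Frailty Scale | yes (5.5, 6.2.2) | yes by 6.1.2, not by 6.2.2 | none named |
| Haemodynamic profile | not shown: first reading is post induction, first dose not timed against it | yes (6.1.2) | none named |
| Laboratory outcomes | not stated | per-patient ever events (6.1.3) | no repeated-measures comparison |
| 6-minute walk | none; discharge and 3 months only | yes (6.1.2) | own rank rule |
| PODS free days (primary) | cannot exist | yes | van Elteren by site |

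Only the SF-36 domains meet all three conditions on the wording. Frailty meets them only if 6.1.2 is right about timing and the default is meant to cover it.

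**Size.** The SAP has no figure of its own for these variables. Its only power figure, 90% with 700 per arm, belongs to the primary outcome and plays no part here.

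Inputs: two-sided alpha 0.05 (5.1), so 1.96; 700 per arm (4.3). Assumptions: correlation rho between baseline and follow-up, taken over a range because the SAP gives none; and, as a benchmark, an effect for which the raw comparison has 80% power.

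- Variance after baseline adjustment, relative to raw: 1 − rho².
- Interval width, relative to raw: √(1 − rho²).
- Patients the raw comparison needs, relative to adjusted: 1/(1 − rho²).
- Benchmark effect: (1.96 + 0.842) × √(2/700) = 0.15 SD.
- Adjusted power: Φ(2.802/√(1 − rho²) − 1.96).

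| rho | Variance ratio | Interval narrower by | Patients needed, raw vs adjusted | Power, from 80% |
|---|---|---|---|---|
| 0.1 | 0.99 | 0.5% | 1.01 | 80.4% |
| 0.3 | 0.91 | 5% | 1.10 | 83.6% |
| 0.5 | 0.75 | 13% | 1.33 | 89.9% |
| 0.7 | 0.51 | 29% | 1.96 | 97.5% |

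Example at rho 0.5: 2.802/√0.75 = 3.235; 3.235 − 1.96 = 1.275; Φ(1.275) = 0.899.

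**Does this carry over to the van Elteren test?** It was simulated with normal scores, an assumed 20 sites of 35 per arm, and 1,000 runs per setting. The test was applied to raw values and to values with the regression on baseline removed.

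| rho | Power, raw | Power, baseline-adjusted |
|---|---|---|
| 0.3 | 0.77 | 0.83 |
| 0.5 | 0.77 | 0.89 |
| 0.7 | 0.78 | 0.96 |

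With no effect, rejection rates were 0.032 to 0.054 over both versions. Both are valid; they differ in precision.

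**The case against.** The strongest reply is that 6.2.3 covers exploratory variables, that 6.2.2 calls even the SF-36 and Barthel analyses mainly descriptive, and that adjusting only for the stratification factor is a legitimate pre-specified choice. No confirmatory conclusion depends on it. That stands, and it keeps the point minor. It does not remove it, because p-values will be produced and read.

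A second reply is that rho, the effect and the 80% starting power are all assumed, and that follow-up scores exist only for survivors, so fewer than 1,400 patients contribute. This also stands for the power column. The variance and interval ratios do not depend on the number of patients, only on rho.

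Third, a reader might infer that the Frailty Scale is a repeated outcome plainly losing precision under the default. The SAP does not support that. Section 6.2.2 leaves frailty out of what is repeated, and if that is right there is no follow-up comparison to improve. The default is also limited to variables not listed earlier, and frailty is listed. What the document shows is conflicting timing and no assigned method.

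Fourth, a reader might extend the point to the haemodynamic profile. That is not supported either: the SAP does not say that the post-induction reading comes before the first dose.

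Finally, one could argue that the SF-36 is named above as an instrument, so its domains are outside the default. But 6.1.2 and 6.2.2 name only the summary scales, and on that argument the domains would have no method at all, which also needs correcting.

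**Conclusion.** The point holds, at low severity. The 6.2.3 default together with 6.2.4 discards a baseline value wherever a variable under the default has one. The SF-36 domains are the one clear instance; the Frailty Scale is conditional on reconciling 6.1.2 with 6.2.2. The variance given up is rho²: 9%, 25% and 49% at rho 0.3, 0.5 and 0.7, and about 1% at 0.1. These values of rho are assumptions, since the SAP reports none. It would be wrong to infer that the comparisons are biased or that their type I error is inflated: randomisation protects both, and the simulation agrees. The primary analysis is not touched, because PODS free days have no baseline and the test already stratifies by site.

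**What to change.** 1. **6.2.2:** extend the constrained longitudinal model to the eight SF-36 domain scores.
2. **6.1.2 and 6.2.2:** reconcile whether the Frailty Scale is collected after baseline. If it is, assign it either the same model or a site-stratified rank ANCOVA on its baseline. If it is not, remove it from the follow-up outcomes in item 11.
3. **6.2.3:** for any other continuous or ordinal variable with a pre-treatment value, use site-stratified rank ANCOVA: within-site ranks of the outcome, adjusted for the within-site rank of the same variable at baseline. Name ordinal variables explicitly; 6.1.4 recognises that scale type, but 6.2.3 gives rules only for categorical and continuous variables. Keep the CMH test for nominal variables.
4. **6.2.4:** permit one exception to the site-only rule, the outcome's own pre-treatment value. The longitudinal model does not strictly need this, since it treats baseline as an outcome; rank ANCOVA does.
5. Leave the primary test unchanged.

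The cost is SAP wording and a little programming. The domain scores need no new data, and for frailty that depends on item 2. The SAP summary table records that no results by arm existed when version 1 was finalised; the change should be dated and made while that is still true. The one drawback is patients without a baseline value. The longitudinal model can keep them through their follow-up scores, but rank ANCOVA needs a stated rule, for instance assigning the site's mean baseline rank without regard to arm.

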6.2.4 Adjustment for covariates

Analysis involving hypothesis testing or creation of confidence intervals will control for site which was the sole stratification factor at randomization. No other covariates will be controlled for.

6.2.5 Assumption checking

The analysis of the primary outcome is non-parametric so no assumptions will be checked. The proportional hazards assumption of 6-month survival will be assessed graphically.

6.2.6 Subgroup analysis

A priori, we expect that there may be a heterogeneity of treatment effect amongst different patient populations. For example, older, sicker patients with less reserve may benefit the most from selenium supplementation. Thus, we plan to do a subgroup analysis comparing the treatment effect in older patients vs. younger patients (based on median age of 70), patients who are frail (Clinical Frailty Scale ≥ 4)⁵ vs. those who are not, patients who are at nutrition risk (positive features of reduced oral intake or recent weight loss) vs. those that are not, in patients that undergo combined procedures (CABG+ value(s) and CABG plus 'other') vs. those that do not have combined procedures, patients who underwent urgent surgery vs. those who underwent elective surgery, patients with moderate-severe baseline chronic kidney disease vs. those that do not, patients with a low ejection fraction (EF <39%) vs. those with EF 40 or greater, and patients with a higher vs lower Euroscore (based on the median score)

and longer vs. shorter CPB (based on median value). In support of these proposed analyses, there is an apparent decline in circulating selenium levels in the elderly in certain populations, which may occur independently of intake.^{6,7} Given the potential differences in baseline selenium levels between North Americans and Europeans (due to selenium depletion in the soil in Europe),⁸ we plan to compare the effect of selenium in the Canadian vs. German subpopulations. Forest plots will be provided to display the effect measure with 95% CIs within each subgroup and sites. For these subgroup analyses, we plan to examine the primary outcome and select secondary outcomes (TTDA, 6 month survival and DAPHD6M). The effect measure for the primary outcome will be the stratified c-index as described in section 6.2. Statistical tests of interaction between treatment arm and subgroup may be performed if treatment effect appears meaningfully different between subgroups.

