4.3 Sample Size Considerations

Sample size copied from published protocol.

The distribution of the control arm was calculated based on a database of patients that underwent cardiac surgery during a 12 month follow up at Aachen University ($n = 1127$) and would meet the inclusion criteria of the current study ($n = 170$). In our dataset, the mean (SD) POD free days was 23.2 (9.2); 4% of the patients died, 6% survived on life-sustaining therapy with 0 POD free days. We checked these numbers with data from the University of Ottawa Heart Institute (Canada), and numbers are consistent with the 4% 30-day mortality rate and the 6% not yet free from life-sustaining therapy by 30 days. We used simulation to estimate the power of applying the Wilcoxon rank-sum test to our primary outcome of PODs free days. The intervention arm was then generated by multiplying the control arm daily rate of liberation from life sustaining therapies by a fixed factor (hazard ratio) but assuming the same 4% mortality rate. The mean days on life-sustaining therapy was then subtracted from 30 to obtain the free days. 10,000 samples were simulated so the power estimate has more than a 95% chance of being accurate to within 1%. Based on the simulation, we would require 700 patients per arm to achieve 90% power at a two-sided $\alpha=0.05$ if the intervention caused as 20% relative increase in the daily rate of liberation from life-sustaining therapy but no change in mortality compared to the control arm. Based on our Aachen data, such an effect size would result in an earlier liberation of life-sustaining therapies and mean increase of 1.5 POD free days (from 23.2 to 24.7 days). We believe such an effect size is plausible and is in line with minimally clinically important differences accepted in other recent major trials in the ICU setting.²

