5.1 Confidence intervals and P-values

95% confidence will be presented for selected key outcomes. P-values will be two-sided without adjustment for multiplicity. However, interpretation of secondary outcomes will consider the multiplicity of tests. There is one pre-specified primary test of efficacy. $P < 0.05$ will be considered statistically significant.

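### Section 6.2.6 examines its numeric effect modifiers only as two-way cuts, with an optional interaction test prompted by how the halves look; a pre-specified continuous interaction would serve better if the effect is graded

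*SAP*

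**What the plan says.** SAP section 6.2.6 gives its reason for looking at subgroups: "older, sicker patients with less reserve may benefit the most from selenium supplementation". It then defines every numeric or ordinal modifier as two groups:

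- age, "comparing the treatment effect in older patients vs. younger patients (based on median age of 70";
- the Clinical Frailty Scale, cut at 4 or above;
- EF, below 39% against 40 or greater;
- EuroSCORE, "patients with a higher vs lower Euroscore (based on the median score";
- cardiopulmonary bypass (CPB) duration, cut at its median.

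The committed output is forest plots with an effect measure and 95% CI in each subgroup. These cover the primary outcome (within-site c-index), time to discharge alive (TTDA), 6-month survival and DAPHD6M. Interaction tests are permitted, not promised, and depend on the effects appearing meaningfully different. No continuous, ordinal or spline interaction appears anywhere in the SAP.

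Section 6.2.4 adjusts for site and nothing else. On error control, section 5.1 says "P-values will be two-sided without adjustment for multiplicity".

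**The concern.** The rationale can be read as a gradient: the older, sicker or frailer the patient, the larger the benefit. A two-way cut answers that question poorly. At a cut of 70, patients aged 69 and 71 fall on opposite sides, while those aged 50 and 69 count as the same. Interaction analyses have little power to begin with, and the cut removes more.

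The conditional test adds to this. Whether a test is run depends on a visual comparison of the same two halves, so a diluted gradient may never be tested. A p-value reported only when the halves already look different is also hard to interpret at its nominal level.

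At stake is the reading of the heterogeneity analyses, not the trial's main conclusion.

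**Working it through.** **1. The plan's own power figure.** The only power statement concerns the overall primary test: "we would require 700 patients per arm to achieve 90% power at a two-sided" 0.05 level, for a "20% relative increase in the daily rate of liberation from life-sustaining therapy".

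- Events needed for a hazard ratio of 1.2: 4 × (1.960 + 1.282)² / (ln 1.2)² ≈ 1265.
- Section 4.3 says "4% of the patients died, 6% survived on life-sustaining therapy with 0 POD free days", so about 90% are liberated: 1265 / 0.90 ≈ 1406 patients, against 1400 planned.
- Cross-check by Wilcoxon simulation, with control data fitted to the stated mean of 23.2, SD of 9.2 and 10% zeros, and the daily liberation probability multiplied by 1.2: power 0.87 to 0.89. If the effect is instead applied as a power of 1.2 on the time-to-liberation curve, power is 0.78 to 0.79. The result depends on a source distribution that is not shown.

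The design figure is thus broadly reproduced. It says nothing about interactions, and the SAP states no power for them.

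**2. Information kept by a cut.** Assume an interaction linear in the modifier X. Replacing X by an indicator keeps a fraction corr(X, indicator)² of the information. For normal X cut at proportion p this is φ(z_p)² / [p(1 − p)].

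- p = 0.5: 0.3989² / 0.25 = 2/π = 0.637. Lost: 36%. In effect 1400 × 0.637 ≈ 891 patients.
- p = 0.2: 0.2800² / 0.16 = 0.490. Lost: 51%.

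**3. Effect on power.** Take an interaction that would have 80% power if X were kept continuous. Power after the cut is Φ[(1.960 + 0.842) × √kept − 1.960].

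| Split | Kept | Power after cut | Simulated, N = 1400 |
|---|---|---|---|
| 50/50 | 0.637 | 61% | 60% |
| 30/70 | 0.576 | 57% | 55% |
| 20/80 | 0.490 | 50% | 50% |
| 15/85 | 0.426 | 45% | 44% |

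The loss stays at or below 50% only if the smaller group holds at least about 21% of patients.

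**4. By modifier.** The SAP gives no distributions, so all of these are assumptions.

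| Modifier | Assumed shape | Information lost |
|---|---|---|
| Age, median split | normal / truncated to 40–90 / uniform | 36% / 34% / 25% |
| EuroSCORE, median split | effect linear in log score (normal) | 36% |
| EuroSCORE, median split | effect linear in raw score, lognormal with log-SD 0.5 to 1.0 | 48% to 73% |
| Frailty, cut at 4 | ordinal, 10% to 50% frail | 32% to 51% |
| EF, cut at 40 | 7% to 27% low | 42% to 71% |

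**5. The reverse case.** If the true effect is a step exactly at the median, the split loses nothing and a linear term keeps only 0.637, a loss of 36%.

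**The case against.** Two-group subgroups with forest plots are conventional. The cuts were fixed before any results by arm were generated (section 1.1), and the frailty cut carries a citation. That limits the worry about where each cut falls. The stated rationale also fits a threshold as well as a gradient, since section 6.2.6 speaks of different patient populations and gives no functional form. All of this stands, and it is why the point is a suggested improvement and not an error.

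Three stronger readings are tempting but unsupported:

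- A reader might infer that the plan tests these modifiers with reduced power. It commits to no test. The power figures describe a test that may never be run, and the optional trigger is arguably the larger weakness of the section.
- A reader might state a single loss for all modifiers, such as a third to a half. The SAP gives no share of patients with low EF or frailty and no EuroSCORE distribution, so no such band can be derived from it.
- A reader might assume that every modifier is stored as a number. Section 5.5 lists age, EuroSCORE II (%) and the baseline frailty scale. It does not name EF, and it leaves further variables to an analytic dictionary that is not shown.

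The change is also not free for PFDs and DAPHD6M. A c-index within a subgroup needs categories, so a continuous interaction there means a model class that the SAP does not otherwise use.

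**Conclusion.** The point holds as a minor, low-cost improvement. Section 6.2.6 looks at five numeric or ordinal modifiers only after a two-way cut, and leaves the interaction test to how the halves appear.

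Under a linear interaction and a roughly normal modifier, a median split costs about 36% of the information, and 80% power becomes about 61%. Over the assumed distributions the loss runs from about 25% to 73%. It is zero if the effect is a step at the cut, in which case a linear term would be the worse choice. The SAP argues for no such step, and the median cuts for EuroSCORE and bypass time come from the sample, not from biology.

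The primary test and its conclusion are unaffected.

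**What to change.** 1. Keep the two-group forest plots for display.
2. Pre-specify an arm × modifier interaction for age, EuroSCORE II (state whether raw or log scale) and the Clinical Frailty Scale (as an ordinal score), and for EF where it was recorded as a number. Report it whatever the forest plots look like.
3. For TTDA and 6-month survival, add the terms to the Cox models with site frailty already planned in section 6.2.2.
4. For PFDs and DAPHD6M, add a proportional-odds model with site, labelled supportive.
5. State in section 6.2.4 that these models include the modifier's main effect, as an exception to adjusting for site alone.
6. Label the interaction results exploratory. Four modifiers on four outcomes give 4 × 4 = 16 unadjusted p-values, so about 16 × 0.05 = 0.8 would fall below 0.05 by chance if there were no heterogeneity.

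Bypass duration is cut in the same way but is left out of this list. It arises after randomization, which section 6.1.1 places before surgery, and that raises a separate question.

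**Cost.** For the Cox models, a few terms and a SAP sentence; age, EuroSCORE II and frailty need no new data. Linearity is assumed and should be checked with a spline. For PFDs and DAPHD6M the cost is an extra model and its proportional-odds assumption, which should be checked too.

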4.1 Trial Design

A randomized, placebo-controlled, double-blind, multicentre definitive trial of 1400 patients across 20 sites in Germany and Canada, which will include the pilot study patients. An industry partner (Biosyn) will provide the product and some additional support for the European sites. Patients will be randomized to receive either a daily perioperative high-dose selenium or placebo until postoperative day 10 (maximum) or upon earlier discharge from ICU.

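### The ejection-fraction subgroup in SAP 6.2.6 has a gap: a patient with a recorded EF from 39% to under 40% belongs to neither group

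*SAP*

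**What the plan says.** Section 6.2.6 of the SAP lists ten subgroup contrasts: age, frailty, nutrition risk, combined procedures, urgency of surgery, chronic kidney disease, ejection fraction, Euroscore, bypass time and country. The ejection-fraction contrast reads "patients with a low ejection fraction (EF <39%) vs. those with EF 40 or greater". This is the only place where the SAP gives an EF cut.

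The same section says what the subgroups are for. On outcomes: "we plan to examine the primary outcome and select secondary outcomes (TTDA, 6 month survival and DAPHD6M". On display: "Forest plots will be provided to display the effect measure with 95% CIs within each subgroup and sites". On formal testing: "Statistical tests of interaction between treatment arm and subgroup may be performed if treatment effect appears meaningfully different between subgroups".

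No rule in the SAP assigns an EF between the two thresholds, and no intention to exclude such patients is stated. Section 6.3 (Missing Data) concerns missing outcomes and does not address this.

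**The concern.** A subgroup contrast that is meant to divide the trial population needs one boundary. Here the low group stops below 39 and the other group starts at 40. Nothing suggests that the interval between them was left out on purpose. In the same sentence, frailty, nutrition risk, combined procedures and kidney disease are each set up as a group against everyone else.

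Two things are at stake, both modest. First, the EF rows of the forest plots would not add up to the analysed population even if EF were recorded for every patient, and a reader would not know why. Second, section 1.3 says the SAP is to give the analyst clear specifications for deriving variables and to record the plan before outcomes are seen by arm. An analyst cannot derive a complete EF variable from this sentence. The analyst must either drop patients or choose a boundary that the plan does not give. Section 7.2 names three outcomes for independent re-analysis and no subgroup derivation, so the planned validation would not necessarily catch the gap.

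**Working it through.** The SAP gives no sample size, power or count for this subgroup, so there is no stated figure to reproduce. The check is whether the two conditions cover every EF value.

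**Inputs**
- Low group: EF < 39 (section 6.2.6).
- Other group: "those with EF 40 or greater", that is EF ≥ 40 (section 6.2.6; read as percent, like the first threshold).
- Planned size, used only for scale: "A randomized, placebo-controlled, double-blind, multicentre definitive trial of 1400 patients across 20 sites in Germany and Canada" (section 4.1).

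**Step 1: coverage.** A value is unassigned if it is not below 39 and not at or above 40, that is if 39 ≤ EF < 40. A value is in both groups if it is below 39 and also at or above 40, which is impossible. The result depends on how finely EF is recorded:

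| Recording step | Values in neither group | Values in both |
|---|---|---|
| 1 point | 39 | none |
| 0.5 point | 39.0, 39.5 | none |
| 0.1 point | 39.0 to 39.9 (ten values) | none |

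Rounding to whole percent therefore shrinks the gap to one value but does not close it.

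**Step 2: possible repairs.**
- Changing the low group to EF ≤ 39 and leaving the upper group alone closes the gap only for whole-percent data. In half-point steps 39.5 stays unassigned, and in 0.1 steps 39.1 to 39.9 do.
- A single boundary c, with EF < c against EF ≥ c, leaves nothing unassigned for any c and any recording step.
- With c = 40 the upper group is as now stated, and the gap patients join the low group.
- With c = 39 the low group is as now stated, and they join the upper group.

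**Step 3: scale.** The number of unassigned patients is 1400 × p, where p is the share with 39 ≤ EF < 40. The SAP does not give p, so a range is assumed:

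| Assumed p | 1400 × p |
|---|---|
| 0.1% | 1.4 |
| 0.5% | 7 |
| 1% | 14 |
| 2% | 28 |
| 3% | 42 |

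The count is thus about 1 to 42 under these assumptions. It cannot be expressed as a share of the low-EF group, because the SAP does not say how large that group is.

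**Step 4: where the patients drop out.** The EF forest-plot rows are planned outright for four outcomes (primary, TTDA, 6-month survival, DAPHD6M), so the loss there is certain for any patient in the gap. The interaction test is optional, so the loss there arises only if the test is run. The main analysis of the primary outcome does not use EF and is untouched.

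**The case against.** The strongest reply is that this is a slip of wording with no practical effect. Since 40 and above is explicit for the upper group, 39 is plainly not in it, and any sensible analyst would code a whole-percent 39 as low. EF is a baseline variable that can be coded blind, and the SAP summary table (section 1.1) says that no outcome results by arm existed when the plan was finalised. The analytic dictionary mentioned in section 6.1.4 is not shown. If EF was captured in bands, the number affected could be zero. Much of this stands, and it is why the point is minor. It does not remove the error: the natural repair is not what the text says, and the text is what the analyst is asked to follow.

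A reader might also infer more than the SAP supports:

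- *That patients are lost from a planned interaction test.* No definite test is planned. It may be done if effects look different.
- *That the loss falls on the group expected to benefit most.* Section 6.2.6 says, by way of example only, that older and sicker patients with less reserve may benefit most. It says nothing about low EF in this respect.
- *That EF is the one loose definition among otherwise clean partitions.* Urgent versus elective names two categories without stating that they cover everyone. The splits by age, Euroscore and bypass time do not say where a patient exactly at the median goes. What sets EF apart is that its two explicit thresholds fail to meet.
- *That the gap invites a data-driven choice of cut-point.* This would require late coding, after by-arm results are available, and for whole-percent data it would also require overriding the explicit upper threshold. It is possible but remote.

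**Conclusion.** The definition is wrong as written: 39 ≤ EF < 40 is in neither group, whatever the recording precision, and nothing else in the SAP assigns those patients. The consequence is limited to the EF rows of the subgroup forest plots for four outcomes and to an EF interaction test if one is performed.

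The size is unknown. The range of about 1 to 42 patients rests on the planned 1400 and on an assumed share of 0.1% to 3%, for which the SAP offers no basis; with banded recording it could be none. The primary test, its population and its significance level are unaffected, and no conclusion of the trial is shown to change. Severity is low.

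**What to change.** Before by-arm results are generated, amend the EF contrast in section 6.2.6 to use one shared cut-point, so that every patient with a recorded EF is in exactly one group. EF <40% versus EF ≥40% is one such definition. It keeps the stated upper group unchanged and works for whole-number and decimal recording alike. Any other single boundary would also close the gap, provided it is fixed in advance.

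The cost is one sentence in the SAP and one line of code. No new data are needed, and the only effect is that the few patients in the gap, if any, are assigned to a group.
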